8.5 SERIOUS ADVERSE EVENTS AND/OR ADVERSE EVENTS REQUIRING DISCONTINUATION OF STUDY DRUG

Any serious adverse event (SAE) or unexpected AE \geq NCI CTCAE Grade 3 that occurs during this study and up to 30 days after discontinuation of study drug must be reported to the Study Medical Monitor within 24 hours of the PI's awareness of the event, whether or not this reaction is considered to be associated with use of the investigational drug. In addition, the occurrence of any AE leading to permanent discontinuation of study drug must also be reported to the Sponsor within 24 hours of the PI's awareness of the event.

Serious adverse events must be scanned and emailed to the Sponsor/Study Medical Monitor.

Email: [contact]

It is expected that the PI will provide or arrange appropriate supportive care for the study patient. A patient experiencing a SAE should be followed clinically until the event resolves, is deemed permanent or no longer clinically significant, or the patient begins an alternative treatment regimen. All telephone and scanned/mailed reports must be followed with a written Serious Adverse Event (SAE) report form within 24 hours of the PI's awareness of serious adverse events and nonserious events which required discontinuation of study drug. The (SAE) report form should be completed and signed by the PI, scanned, and sent by email to the Sponsor as described above. The SAE Report Form is distinct and separate from the adverse event form included in the case report form.

Grades for all SAEs and AEs, regardless of whether they trigger expedited reporting or not, must still be captured by the CRF.

8.6 FOLLOW-UP OF ADVERSE EVENTS

Adverse events, which are identified on the last scheduled visit, must be recorded on the AE CRF page and reported to the Sponsor according to the procedures outlined in [Section 8.4](#).

Patients with unresolved previously reported AEs or new AEs identified on the last scheduled visit should be followed by the PI until the AEs resolve, are deemed permanent or no longer clinically significant, or the patient begins an alternative treatment regimen. Resolution means the patient has returned to his/her baseline state of health or the PI does not expect any further improvement or worsening of the adverse event. The PI should continue to report any significant follow-up information to the Sponsor up to the point the event has resolved. Any adverse events reported by the patient to the PI which occur after the last scheduled visit, and are determined by the PI to be reasonably associated with the use of the study drug or meet the criteria of a reportable adverse event as described above, should be reported to the Sponsor.

Patients withdrawn from the study with an ongoing AE or SAE must be followed clinically until the event is resolved, deemed permanent or no longer clinically significant, or the patient begins an alternative treatment regimen. A stable adverse event is defined as an event, which is not expected to change in nature, severity, or frequency. The PI should continue to report any significant follow-up information to the Sponsor.

8.7 PATIENT DEATHS

Every effort will be made in the case of patients who die to determine the cause of death. Information regarding a patient who dies more than 30 days after receiving study drug may be recorded on a Death Report Form (no SAE report is required). An SAE report is recorded only if the event leading up to the patient's death began within 30 days of the last administration of study drug.

The Death Report Form is distinct and separate from the adverse event form included in the case report form.

8.8 REPORTING ADVERSE EVENTS TO THE REGULATORY AUTHORITIES

The Sponsor will be responsible for reporting adverse events to the Food and Drug Administration (FDA) as described in 21 CFR Section 312.32 (IND Safety Reports) and to other Regulatory Authorities according to local regulations.

In addition, the PI is required by FDA regulations to notify the Institutional Review Board (IRB) promptly of all unexpected SAEs occurring at the investigator's study site. The PI is also required by FDA regulations to forward the IRB all IND Safety Reports received from the sponsor.

The Sponsor will also report SAEs in compliance with local regulatory requirements.

9. STUDY DRUG MANAGEMENT

9.1 STUDY DRUGS

The investigational study drug, alvocidib, will be provided to the PI by the Sponsor or designee.

Alvocidib is supplied for parenteral administration as a sterile, nonpyrogenic, injectable, clear pale yellow to yellow-colored, 10 mg/mL solution, which is packaged in glass vials fitted with coated rubber closures crimped with an aluminum seal and blue plastic cap. Each vial contains 50 mg of alvocidib (calculated with reference to the active moiety). The fill volume has been established to ensure removal of 5 mL. The pH of the solution ranges between 2.7 and 3.3. The solution contains the following excipients: water for injection, glacial acetic acid, and sodium hydroxide (as needed to reach the targeted pH).

Decitabine and azacitidine are approved pharmaceutical products and will be provided by commercially available sources.

Decitabine for Injection is a white to almost-white sterile, lyophilized powder supplied in a clear colorless glass vial. Each 20-mL, single-dose, glass vial contains 50 mg decitabine, 68 mg monobasic potassium phosphate (potassium dihydrogen phosphate) and 11.6 mg sodium hydroxide sterile [29].

Azacitidine for injection is a white to off-white solid. Each 100-mg, single-dose vial contains 100 mg of azacitidine and 100 mg mannitol as a sterile lyophilized powder [30].

9.2 STUDY DRUG DISPENSING AND ACCOUNTABILITY

Alvocidib will be provided by the Sponsor to study centers as an investigational drug. The label and package for the drug product will be prepared in accordance with current regulatory requirements. The Investigator or designee will inventory and acknowledge receipt of all shipments of study drugs. The study drugs must be kept in a locked area with access restricted to designated study personnel.

An accurate and current accounting of the dispensing of the study drugs for each patient will be maintained on an ongoing basis by a member of the study site staff in a drug accountability log or equivalent document and will be verified by the sponsor's study monitor. All drug supplies, including unused study drug, must be accounted for. A final inventory of the total amount of drug received at each study site against the amount used and returned must be recorded in the study drug accountability log or an equivalent document. Inventory and dispense records must be readily available for inspection by the study monitor and/or auditor, and open to government inspection at any time. Study drug destruction will be handled by the sites of open/used vials. Unopened study

drug vials should be returned to the Sponsor or ***the Contract Research Organization (CRO) and/or drug may be authorized for destruction onsite*** at the end of the study only after full drug accountability has been completed by the study monitor.

9.3 PREPARATION AND ADMINISTRATION

Alvocidib is to be diluted with either 0.9% Sodium Chloride Injection, United States Pharmacopeia (USP), or 5% Dextrose Injection, USP, prior to infusion, providing solutions of 0.09 to 1.0 mg/mL alvocidib. The diluted solution should be administered according to treatment schedule provided in [Section 4.4.2.1](#).

Decitabine should be aseptically reconstituted with 10 mL of Sterile Water for Injection, USP; upon reconstitution, each mL contains approximately 5.0 mg of decitabine at pH 6.7-7.3 [29]. Immediately after reconstitution, the solution should be further diluted with 0.9% Sodium Chloride Injection or 5% Dextrose Injection to a final drug concentration of 0.1-1.0 mg/mL. Unless used within 15 minutes of reconstitution, the diluted solution must be prepared using cold (2°C to 8°C) infusion fluids and stored at 2°C to 8°C (36°F to 46°F) for up to a maximum of 4 hours until administration. The diluted solution should be administered according to treatment schedule provided in [Section 4.4.2.1](#).

Azacitidine should be aseptically reconstituted with Sterile Water for Injection, USP, per the US prescribing information and based on intended route of administration [30]. (Azacitidine is incompatible with 5% Dextrose solutions, Hespan, or solutions that contain bicarbonate. These solutions have the potential to increase the rate of degradation of azacitidine and should therefore be avoided). The total dose should be administered according to treatment schedule provided in [Section 4.4.2.1](#). Administration must be completed within 1 hour of reconstitution of the vial(s).

Decitabine and azacitidine are approved pharmaceutical products. Complete instructions and training on the proper preparation and administration of all study drugs will be provided to study sites in the Pharmacy Manual.

9.4 STORAGE AT STUDY CENTER

- Alvocidib should be stored at USP controlled room temperature (ie, 20°C to 25°C [68°F to 77°F]) with permitted excursions between 2°C to 30°C (36°F to 86°F)
- Decitabine should be stored at 25°C (77°F); excursions permitted to 15°C to 30°C (59°F to 86°F)
- Azacitidine unreconstituted vials should be stored at 25°C (77°F); excursions permitted to 15°C to 30°C (59°F to 86°F)

9.5 COMPLIANCE

Study drugs will be administered by trained staff at the treatment site(s).

10. RECORD MANAGEMENT

10.1 DATA COLLECTION

The Investigator must maintain required records for all study subjects. Case report forms are used to record clinical study data and are an integral part of the study and subsequent reports. Data for this study will be recorded in the subject's source document and into an electronic Case Report Form (eCRF) system that must be kept current to reflect patient status during each part of the study. Patients are not to be identified by name on the eCRF. Appropriately coded identification (site number, patient identification number, and patient initials) should be used.

Electronic CRFs are not to be used as source documents. Investigators must keep accurate separate records (other than the CRFs) of all subjects' visits, being sure to include all pertinent study related information. A statement should be made indicating that the subjects have been enrolled in this clinical study and have provided written Informed Consent. Any adverse events must be thoroughly documented. Results of any diagnostic tests conducted during the study should also be included in the source documentation.

All data should be recorded completely and promptly in the eCRFs as soon after the visit as possible, but no later than 5 days. All queries are to be answered within 3 days of query date.

The PI will allow the Sponsor or its representative, or an appropriate representative of the regulatory authorities to inspect study documents (eg, consent forms, drug distribution forms, institutional review board/independent ethics committee [IRB/IEC] approval) and pertinent hospital or clinic records for confirmation of data throughout the study period.

10.2 SOURCE DOCUMENT MAINTENANCE

Source documents are defined as the results of original observations and activities of a clinical investigation. Source documents may include, but are not limited to, hospital medical records, study progress notes, consent forms, computer printouts, laboratory data and recorded data from automated instruments. All source documents produced in this study will be maintained by the PI and made available for inspection by representatives of the Sponsor or the Regulatory Authorities. The original signed informed consent form for each participating patient shall be filed with the records kept by the PI with a copy filed in the patient's medical records, and a copy given to the patient.

A source document is an original record of information, also known as source data, which is necessary for the reconstruction and evaluation of a clinical trial. The purpose of source documents is to provide proof of a participant's existence, confirm that protocol-related procedures were completed and conducted per protocol and to verify that data reported in the study CRFs are accurate.

Source documents at a clinical trial site may be maintained in paper or electronic format and typically contain the types of information below. If electronic source documents are used, sponsor and study monitors will be given access to verify study data.

Source documents can include, but are not limited to:

- Notes from clinic physicians, nurses, and other study staff
- Reports of procedures and tests
- Flow sheets, checklists, and worksheets
- Subject diaries, study calendars
- Pharmacy records, accountability logs, shipping receipts
- Study notes or memos to file
- Documented telephone calls, emails, faxes
- Hospital admission forms and discharge summaries
- Sponsor/site-generated study source document templates

Source documents must meet five fundamental principles of data quality (“ALCOA”). They must be:

- **Attributable** – The data originator is identified. If data needs to be amended, the amender is identified.
- **Legible** – The source document must be readable. If handwritten, black or blue ink must be used, never pencil.
- **Contemporaneous** – The document must be signed and dated when the information is first recorded, with any updates or corrections noted in real time as well.
- **Original** – The document must be the first place the information is recorded.
- **Accurate** – The information must be error-free, and any conflicts with data recorded elsewhere must be reconciled.

10.3 RECORD MAINTENANCE

The Investigator must retain a comprehensive and centralized filing system of all clinical study-related documentation that is suitable for inspection by the Sponsor and representatives of regulatory authorities.

The Investigator must retain essential study documents (as specified in Section 8 of ICH-GCP and as required by the applicable regulatory requirements) until at least 2 years after the last approval of a marketing application. Patient files and other source data (including copies of protocols, CRFs, original reports of test results, agent-dispensing logs, correspondence, records of informed consent, and other documents pertaining to the conduct of the trial) must be kept for the maximum period of time permitted by the institution.

No trial document will be destroyed without prior written agreement between the Sponsor and the Investigator. Should the Investigator wish to assign the trial records to another party or move them to another location, written agreement must be obtained from the Sponsor.

The PI shall take responsibility for maintaining adequate and accurate hard-copy source documents of all observations and data generated during this study, including any data clarification forms (DCFs) received from the Sponsor. Such documentation is subject to inspection by the Sponsor and the FDA or other Regulatory Authorities.

10.4 STUDY CENTER FILE MANAGEMENT

It will be the responsibility of the PI to assure that the study file at the center is maintained. The study file for this protocol will contain, but will not be limited to, the information listed below:

- Investigator's Brochure, current version, and all versions provided during the study period.
- Final study protocol.
- Protocol amendments (if applicable).
- Original informed consent form (blank).
- Revised informed consent forms and/or all addenda (if applicable).
- Copy of signed FDA Form(s) 1572
- Curricula Vitae and medical licenses of PI and Subinvestigators.
- Financial Disclosure Form of PI and Subinvestigators (if applicable).

- Department of Health and Human Services Number for IRB, or other documentation of IRB compliance with FDA regulation (United States sites).
- Documentation of IRB/IEC approval of protocol, consent form, any protocol amendments and any consent form revisions.
- Annual IRB/IEC updates and approvals.
- All correspondence between the PI, IRB/IEC and Sponsor or Sponsor's representative relating to study conduct.
- Copies of all 7-day and 15-day Safety Reports submitted to the Regulatory Authorities (provided by Sponsor) and IRB/IEC correspondence documenting their submission.
- Laboratory certifications.
- Normal laboratory value ranges for tests required by the protocol for all laboratories that are utilized.
- Clinical Research Associate (CRA) monitoring log.
- List of signatures and Delegation of Authority for all study personnel
- Drug invoices for both receipt and return of study drug, as well as drug inventory/accountability records.

11. STATISTICAL CONSIDERATIONS

11.1 GENERAL CONSIDERATIONS

Protocol TPI-ALV-102 is a Phase 1b / 2, multicenter, open-label study in which Phase 1b will employ the 3+3 dose-escalation design, dose expansion at MTD/RP2D, and Phase 2 utilizing the Simon 2-stage minimax design [27].

Results of statistical analyses, descriptive statistics, and supporting listings will be presented by study phase (Phase 1b and Phase 2) and within alvocidib dose level. In addition, overall statistics will be calculated for Phase 1b patients across all alvocidib dose levels and for the total study population (ie, regardless of study phase).

Statistical analysis for all safety and efficacy parameters will be primarily descriptive in nature. Categorical variables will be summarized by frequency distributions (number and percentages of patients), continuous variables will be summarized by mean, standard deviation, median, minimum, maximum, and time-to-event variables will be summarized using Kaplan-Meier methods and figures for the estimated median time. No formal statistical hypothesis testing is planned; however, if exploratory analyses are conducted and confidence intervals (CIs) are provided for estimates, the 95% confidence intervals are consistent with a 2-sided 5% significance level. All analyses, summaries, and listings will be performed using SAS software (version 9.4 or higher).

A detailed methodology for summary and statistical analysis of the data collected in this study will be documented in a Statistical Analysis Plan (SAP) that will be finalized prior to database lock. The SAP may modify the data analysis plans outlined in the protocol; and if so, will be clearly documented in the SAP. Any major modifications of the study design or study endpoints and/or its analysis will also be reflected in a protocol amendment.

11.2 SAMPLE SIZE CONSIDERATIONS

Phase 1b

Patients will be enrolled in cohorts of 3-6 patients. Escalation of the alvocidib dose will follow a standard 3+3 design with sequential cohorts of 3 patients treated with incrementally higher doses of alvocidib until a DLT is observed and the MTD is established ([Section 4.5.3](#)). Per the standard oncology 3+3 Phase 1 dose escalation design, the total number of patients to be enrolled cannot be precisely determined as the sample size is dependent upon the observed safety profile, which will determine the number of patients per dose cohort, as well as the number of dose escalations required to achieve the MTD. It is anticipated that a maximum of 24 patients will be required to reach MTD and determine the RP2D.

The MTD is defined as the dose at which ≤ 1 of 6 patients experience a DLT during Cycle 1 with the next higher dose having at least 2 of 3 to 6 patients experiencing a DLT during Cycle 1. Adverse events meeting the definition of DLT during Cycles 2+ will be taken into consideration when evaluating dose escalation.

Once the MTD or preliminary RP2D of alvocidib administered via hybrid dosing (ie, IV bolus followed by IVI) is identified, 2 cohorts of at least 3 patients each will receive AZA followed in sequence by alvocidib with the total dose of alvocidib administered by **30- to 60-minute** IVI.

Expansion at MTD

Once the MTD or preliminary RP2D of alvocidib administered by **30- to 60-minute** IVI is determined, up to 25 patients will be enrolled in an Expansion cohort to receive alvocidib following either DEC or AZA to confirm safety, explore potential biomarkers, and evaluate potential signals of alvocidib activity. Once this Expansion cohort is completed, the study will progress to Phase 2.

Phase 2

Stopping Rules based on Efficacy

The statistical power calculations for Phase 2 are based on the Simon 2-stage minimax design [27].

- Stage 1: Up to 15 evaluable patients will be enrolled and treated at the RP2D identified in the Phase 1b study. Stage 2 may be initiated at any point after confirming a response (CR/CRi/CRmarrow/PR/HI) in two Stage 1 patients. If there is ≤ 1 responder among 15 evaluable Stage-1 patients, the study will be stopped after Stage 1.
- Stage 2: Ten patients will be enrolled to bring the total enrollment in Phase 2 (including Stage-1 patients) to 25 evaluable patients. Stage-2 patients will also receive the RP2D dose of alvocidib administered by **30- to 60-minute** IVI identified in the Phase 1b study. If 6 or more responses are observed in 25 patients, the conclusion will be that the combination regimen is worthy of further investigation. When the true response rate of 30% (alternative hypothesis) is tested against the null hypothesis response rate of 10%; this design yields a Type I error rate of 0.05 and power of 80%.

Any patient who withdraws from Stage 1 or 2 for treatment-related toxicity or disease progression or dies prior to being evaluated for response, they will be considered a non-responder. Patients who drop out for other reasons prior to being assessed for response will be considered unevaluable and may be

replaced. Enrollment into Phase 2 may be stopped at any point once ≥ 6 patients have had a response to treatment, but the maximum enrollment in Phase 2 will be 25 evaluable patients.

Stopping Rules based on Safety

The study may be stopped early during Phase 2 in the event of unacceptable toxicities. Early stopping rules for safety are based on a Sequential Probability Ratio Test (SPRT) with a baseline toxicity rate of 5%; an upper ceiling of unacceptable toxicity of 20% (ie, toxicities meeting one or more DLT criteria as stated in [Section 4.5.3](#)); and alpha=0.05 with power=80%.

The study will be stopped if unacceptable toxicities are observed in:

- 2 of the first 2 patients
- 3 of the first 11 patients
- 4 of the first 20 patients
- 5 of the first 29 patients (Ph 2 study to enroll maximum of 25 patients, but considering possible replacement patients)

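### The Phase 2 toxicity stopping rule is quoted at 80% power, but capped at 25 patients it stops a 20%-toxic regimen only 67% of the time (76% at 29)

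*Protocol*

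**What the plan says.** Protocol section 11.2 (Stopping Rules based on Safety) states: "Early stopping rules for safety are based on a Sequential Probability Ratio Test (SPRT"), with a "baseline toxicity rate of 5" per cent, "an upper ceiling of unacceptable toxicity of 20" per cent, "and alpha=0.05 with power=80" per cent. A toxicity counts if it meets a DLT criterion of section 4.5.3. The study stops at "2 of the first 2 patients", "3 of the first 11 patients", "4 of the first 20 patients" or "5 of the first 29 patients (Ph 2 study to enroll maximum of 25 patients, but considering possible replacement patients").

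The same section caps Phase 2 at 25 evaluable patients. Patients who drop out before response assessment, for reasons other than treatment-related toxicity, progression or death, may be replaced. The rule is repeated in the synopsis, in protocol sections 4.1 and 4.4.2.3, and in SAP sections 2 and 4. None of these places calls the 80% nominal, limits it to an uncapped test, or gives the rule's properties under the cap.

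**The concern.** Wald's error rates hold approximately for a sequential test that continues until it reaches one of its two boundaries. Ending the test at a fixed number of patients removes the later chances to cross the upper boundary. Power at the alternative then falls unless the limits are recalculated for that maximum. Here the limits are the open-ended ones, while the trial ends at 25 evaluable patients, or about 29 with replacements.

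This is the only numerical toxicity stopping rule for Phase 2, and section 6.4 treats a data safety monitoring board as optional. A sponsor or ethics board relying on the text would expect a regimen at the 20% ceiling to be stopped four times in five.

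**Working it through.** **Inputs**, all from protocol section 11.2: p0 = 0.05, p1 = 0.20, alpha = 0.05, beta = 1 − 0.80 = 0.20, limits 2/2, 3/11, 4/20 and 5/29, maximum 25 evaluable patients (29 allowing for replacements).

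**Step 1: reproduce the limits.** The log likelihood ratio moves as follows.

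- Per toxicity: ln(0.20/0.05) = +1.3863
- Per patient without toxicity: ln(0.80/0.95) = −0.1719
- Upper limit: ln((1 − beta)/alpha) = ln(0.80/0.05) = ln 16 = 2.7726

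With d toxicities in n patients, the test stops when 1.3863d − 0.1719(n − d) ≥ 2.7726, that is, when d ≥ (2.7726 + 0.1719n)/1.5581. The largest n at which 2, 3, 4 and 5 toxicities suffice is 2, 11, 20 and 29. This is the listed rule exactly, so the rule is identified without ambiguity.

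**Step 2: exact stopping probability.** Let f(n, d) be the probability of having d toxicities after n patients without having stopped. Then

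f(n, d) = (1 − p) f(n−1, d) + p f(n−1, d−1).

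At each n, the probability at or above the threshold is moved to the stopped state. The threshold is 2 at n = 2, 3 for n = 3–11, 4 for n = 12–20, and 5 for n = 21–29. For example, at p = 0.20 the probability of stopping at n = 2 is 0.20² = 0.04. Cumulative results:

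| Patients | P(stop), 20% toxicity | P(stop), 5% toxicity |
|---|---|---|
| 2 | 0.040 | 0.0025 |
| 11 | 0.388 | 0.017 |
| 15 | 0.447 | 0.018 |
| 20 | 0.621 | 0.026 |
| 25 | **0.675** | **0.027** |
| 29 | **0.760** | **0.031** |

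The probability of a miss at 20% toxicity is 1 − 0.675 = 0.325 with 25 patients and 1 − 0.760 = 0.240 with 29, against 0.20 as stated. A simulation of 400,000 trials gave 0.676 and 0.761.

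**Step 3: does another reading give 80%?**

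- Looks only at 2, 11, 20 and 25 patients: 67.5%. With 29 as the last look: 76.0%.
- Adding the test's lower (acceptance) boundary: 65.3% at 25 and 71.9% at 29.
- Open-ended test with both boundaries and no cap: 82.5%, with a false-stop rate of 3.4%. Of the readings tried, only this one reaches 80%, and the trial does not run it.
- Upper boundary alone, carried on past 29: still 76.0% at 30 patients and 80.5% at 35.

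**Step 4: what the capped rule can detect.** Stopping probability reaches 80% at a true toxicity rate of 23.4% with 25 patients, or 21.1% with 29. A search over monotone boundaries at 25 patients with a false-stop rate of at most 5% peaks at 78.7%. The stated pair of 5% and 80% is therefore not attainable at 25 patients by a rule of this kind.

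**The case against.** The strongest reply is that the plan lists alpha and power as inputs to the test. It says the rules are based on an SPRT with those values, whereas the Simon design in the same section is said to yield its error rate and power. Read as inputs, the four values reproduce the limits exactly. That explains where the 80% comes from. It does not tell a reader that the capped rule falls short, and the figure stands unqualified beside the cap.

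Second, the cap counts patients evaluable for response, while toxicity is counted in everyone treated, so replacements push the number above 25. This stands: the relevant figure lies between 67.5% with no replacements and 76.0% with four. Both are below 80%.

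Third, the 44.7% at 15 patients says little if Phase 2 ends there for lack of response, because the regimen is then abandoned anyway. That is fair. The figure matters more under the provision that lets enrollment stop once six patients have responded, where a regimen could go forward on few patients.

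Finally, other safeguards exist: individual discontinuation after a DLT (section 4.5.4) and termination for unacceptable risk (section 6.4). SAP section 1 reports study closure, and SAP section 2 reports no Phase 2 patients. These points limit the practical consequence but do not make the figure right.

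**Conclusion.** Wrong as written. The limits are correctly derived, but the power attached to them is not a property of the capped rule. At 20% toxicity the rule stops 67.5% of the time with 25 patients and 76.0% with 29, a shortfall of 12.5 and 4.0 percentage points. With 25 patients the miss probability is about 1.6 times the stated one (0.325/0.20). The rule is also more conservative at 5% toxicity than stated (2.7% to 3.1% against 5%).

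The figures assume independent patients with a common toxicity probability, outcomes counted in order, and a stop as soon as a limit is reached. No figure from outside the documents is needed. The point concerns the stated design only. It still needs correcting in the SAP, which declares that it supersedes the protocol's statistical considerations.

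**What to change.** In the protocol synopsis and sections 4.1, 4.4.2.3 and 11.2, and in SAP sections 2 and 4, replace the alpha and power statement with the exact properties. The probability of stopping is about 3% at a true toxicity rate of 5%. At 20% it is about 67% with 25 patients and about 76% with 29. If the nominal values are kept to show how the limits were obtained, label them as the parameters of an uncapped SPRT.

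If the sponsor wants higher detection, the limits would have to be re-derived for a 25-patient maximum. Even then, about 79% is the most available at a false-stop rate of 5% or less, so 80% should not be claimed for that size. Whether to change the limits is the sponsor's decision and is not needed to correct the statement.

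The cost is wording and a less favourable stated figure. No patients, visits or analyses are added.
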